4.2.1. Justification of Design and Control Group

Currently, there are no approved pharmacologic therapies for this disease. The recommended first-line nonpharmacologic therapy is lifestyle modification through dietary modification and increased physical activity (*Ratziu, 2013*).

Based on nonclinical and *in vitro* data, EDP-305 is an FXR agonist which plays an essential role in the feedback regulation of BA biosynthesis and given the critical role BAs play in liver homeostasis, FXR has become a target for therapeutic intervention in NASH.

[REDACTED]

This Phase 2 study aims to evaluate safety, tolerability, and PK/PD (ie, dose selection) of the investigational novel FXR agonist, EDP-305 in a targeted patient population with presumptive presence of NASH by either a prior liver biopsy or phenotypic characteristics but no liver biopsy at entry. Subjects will have confirmed presence of NASH by histologic evidence on a prior liver biopsy within 24 months and elevated ALT, OR phenotypic diagnosis of NASH based on elevated ALT, BMI (>25 kg/m² or >23 kg/m² for Asian-Americans), and diagnosis of T2DM or pre-diabetes. These subjects at high risk for NASH will be assessed based on evidence of fatty liver, two components of the metabolic syndrome, and evidence of liver fat and stiffness by imaging.

This double-blind phase of this study is being conducted for 12 weeks. Based on the mechanism of EDP-305 and, on observed data in other short-term treatment Phase 2 studies that were published with similar therapies (*Neuschwander-Tetri et al., 2015*), the Sponsor believes that liver enzyme reductions and change in noninvasive biomarkers (imaging and metabolic/mechanistic markers) will be seen after >1 month of therapy.

[REDACTED]

The purpose of the double-blind design is to obtain the most unbiased assessment of clinical safety and efficacy with the doses being studied. To assess changes in liver fat and fibrosis an MRI and MRE will be conducted during the screening period and at the end of treatment. Additionally, markers for liver fibrosis and inflammation, cardiovascular markers, and biomarkers for NASH will be evaluated throughout the study and changes from baseline evaluated.

[REDACTED]

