3.2 Randomization and blinding

3.2.1 Randomization

Subjects will be randomized to study treatment using an Interactive Web Response System (IWRS). Subjects will be stratified initially by prior liver biopsy vs no prior liver biopsy. Subjects will be randomized to the treatment groups shown below:

- Treatment Group 1 (N=50); EDP-305 1 mg orally for 12 weeks
- Treatment Group 2 (N=50); EDP-305 2.5 mg orally for 12 weeks

- Treatment Group 3 (N=25); Placebo (PBO) orally for 12 weeks

A minimum of 10 subjects per treatment group will be included in the PK/PD substudy. The randomization code will be produced by Enanta (or designee). The Enanta unblinded biostatistician or designee will review and approve the final randomization list.

During the Screening period, subjects will be identified by a unique screening number assigned by the clinical site. Subjects who have completed screening assessments and are eligible for participation in the study will be randomized before the first dose of study drug (Day -1 or Day 1) and assigned a unique subject number which will be used to identify the subject throughout the study.

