8.6.4.2 Subgroup Analyses

Subgroup analyses will be performed on selected outcomes in subgroups of interest. All subgroup analyses will be exploratory in nature. As the interest will be on how different treatment regimens work in a specific subgroup, instead of whether the treatment differences are the same across different subgroups, the subgroup analyses will be performed by analyzing the outcome data in different subgroups, instead of analyzing the outcome data in the whole population with subgroup factors included in the analyses model.

Subgroup analyses will be performed for the primary endpoint and the secondary endpoints to determine whether significant differences exist in primary and secondary endpoint results between subgroups.

These subgroup analyses will be carried out using the subjects from the efficacy population.

The list of potential subgroups (with applicable definitions in parentheses) includes the following:

- MRE Week 12 response: (<15% reduction vs \geq 15% reduction in percentage of change from baseline)
- MRI-PDF Week 12 response: (<30% reduction vs \geq 30% reduction in percentage of change from baseline)
- Both MRE Week 12 response (\geq 15% reduction in percentage of change from baseline) and MRI-PDF Week 12 response (\geq 30% reduction in percentage of change from baseline) vs non-response
- NASH Diagnosis (biopsy vs phenotype)
- ALT Week 12 Category (\geq 0 change from baseline
 - (0--10] change from baseline
 - (-10--20] change from baseline
 - (-20--30] change from baseline
 - (-30--40] change from baseline
 - <-40 change from baseline) AND same ALT categories for percent change from baseline

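### SAP 8.6.4.2 says it will look for differences between subgroups but plans no analysis that compares treatment effects between them

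*SAP*

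**What the plan says.** SAP 8.6.4.2 opens by labelling the work: "All subgroup analyses will be exploratory in nature". It then states that interest lies in how the regimens work within a specific subgroup, "instead of whether the treatment differences are the same across different subgroups". On that ground it chooses a separate fit in each subgroup. The joint model is the alternative it passes over, in these words: "instead of analyzing the outcome data in the whole population with subgroup factors included in the analyses model".

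The next paragraph gives a different purpose for the primary and secondary endpoints: "to determine whether significant differences exist in primary and secondary endpoint results between subgroups".

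The list of potential subgroups has one baseline item, NASH diagnosis by biopsy or phenotype. The rest are Week 12 response categories for MRE, MRI-PDFF and ALT. NASH diagnosis corresponds to the randomization stratum in SAP 3.2.1: "Subjects will be stratified initially by prior liver biopsy vs no prior liver biopsy". It also reflects the two entry routes in Protocol 4.2.1, which describes a population with "presumptive presence of NASH by either a prior liver biopsy or phenotypic characteristics but no liver biopsy at entry".

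SAP 8.6.1 describes the efficacy ANCOVA: treatment and baseline, each dose against placebo, with 95% confidence intervals and p-values. SAP 8.6.1.1 makes no multiplicity adjustment. The nearest thing to a subgroup term is in SAP 8.6.3.1, where MRI-PDFF response is added to an ANCOVA as a fixed effect. That is a main effect, not an interaction.

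**The concern.** The method chosen in the first paragraph cannot meet the aim stated in the second. Two separate ANCOVAs give two sets of p-values and no estimate of how far the treatment effects differ. A result that is significant in one subgroup and not in the other is not evidence of a difference, because the two subgroups can differ in size and each has much less power than the whole trial.

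This matters most for NASH diagnosis. The trial enrols subjects with histologic NASH alongside subjects diagnosed by phenotype alone, so whether the second group responds like the first is an obvious question. With only the planned output, a reader looking for the promised between-subgroup answer has little to use except the pair of p-values, and could report an effect in one diagnostic group only when the true effect is the same in both.

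**Working it through.** **Inputs.** From SAP 5: 44 per dose group, 22 placebo, mean difference in ALT change -30, SD 40, two-sided alpha 0.05, two-sample t-test, stated power 80.438%. The biopsy:phenotype split is not in the documents, so 50:50 to 80:20 is assumed. The subgroup receiving the larger share does not affect the result.

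**Reproducing the plan's power.** The noncentrality is 30 / (40 × √(1/44 + 1/22)) = 2.87 with 64 df, which gives 80.8%. This agrees with the stated figure to within 0.4 points.

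**Identical effect in both subgroups.** Let p1 and p2 be the noncentral-t power in each subgroup. The subgroups contain different subjects, so for one dose:

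P(exactly one significant) = p1(1 - p2) + p2(1 - p1)

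| Assumed split | Subgroup sizes (dose:placebo) | p1 | p2 | Exactly one significant |
|---|---|---|---|---|
| 50:50 | 22:11 and 22:11 | 50.3% | 50.3% | 50% |
| 70:30 | 31:15 and 13:7 | 64.5% | 32.8% | 55% |
| 80:20 | 35:18 and 9:4 | 71.8% | 20.7% | 63% |

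For the last row: 0.718 × 0.793 + 0.207 × 0.282 = 0.628.

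In simulation (20,000 trials per split), at least one of the two doses was discordant in 70% to 80% of trials.

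**Sensitivity to baseline adjustment.** The planned model is an ANCOVA, so the residual SD may be below 40. How far below is an assumption.

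| Residual SD | 50:50 | 70:30 | 80:20 |
|---|---|---|---|
| 30 | 38% | 48% | 64% |
| 25 | 21% | 34% | 55% |

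**The interaction test under the same identical effect.** Simulated false-positive rates were 4.7% to 5.1% per dose comparison, and 8% to 9% for at least one of the two doses.

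**Precision of the interaction contrast.** SE = SD × √(1/a1 + 1/a0 + 1/b1 + 1/b0), where a and b are the two subgroups and 1 and 0 are dose and placebo.

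- 50:50: 40 × √(1/22 + 1/11 + 1/22 + 1/11) = 20.9 IU/L
- 80:20: 40 × √(1/35 + 1/18 + 1/9 + 1/4) = 26.7 IU/L

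The difference detectable with 80% power is (1.960 + 0.842) × SE, or about 58 to 75 IU/L. If the drug had its full effect of 30 in one subgroup and none in the other, the test would detect this about 30% of the time at 50:50 and 20% at 80:20 (normal approximation). At SD 30 the SE and the detectable difference both shrink by 30/40, to about 44 to 56 IU/L detectable.

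**The case against.** The strongest reply is that the 50% to 63% is not the error rate of anything the SAP plans. Section 8.6.4.2 gives no rule for declaring a subgroup difference and never says p-values will be compared. If the ANCOVA of 8.6.1 is used within subgroups, estimates and confidence intervals will be on the page too. This stands: the figures describe a misreading that the text invites, and are conditional on it. What remains is a stated aim with no method behind it.

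A reader might also infer that the SAP forbids a joint model. The documents do not support that. The SAP prefers separate fits, gives a reason, labels the work exploratory, and in 8.6.3.1 adds a subgroup to an ANCOVA itself.

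The disputed sentence can be read as concerning endpoint results rather than treatment effects, for example outcomes of imaging responders against non-responders. That is a fair reading for the Week 12 categories. For NASH diagnosis the sentence still promises a between-subgroup comparison, and none is specified.

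Finally, the interaction test is weak at this sample size, and a non-significant result is easily misread as equal effects. That is correct and belongs beside the 5% false-positive rate. It is a reason to show the contrast with its interval; separate p-values hide the same uncertainty.

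**Conclusion.** The two paragraphs of SAP 8.6.4.2 conflict, and following the plan as written cannot validly meet the second aim. No treatment-by-subgroup term is planned anywhere in the SAP.

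For NASH diagnosis, comparing within-subgroup p-values would suggest a difference that does not exist in about 50% to 63% of trials per dose, against about 5% with an interaction test. This assumes the planning effect of -30 holds equally in both subgroups, SD 40, 44 versus 22, and a split between 50:50 and 80:20. With residual SD of 25 to 30 the range is about 21% to 64%.

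It would go too far to conclude that the analysis itself will return a false answer at these rates, since no comparison rule is planned. Nor does the point touch the primary analysis. It concerns an exploratory section, where the remedy is cheap and gives a better answer than the plan does.

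**What to change.** For NASH diagnosis, fit one exploratory ANCOVA in the whole efficacy population with treatment, baseline, diagnosis and treatment-by-diagnosis. Report the interaction contrast for each dose versus placebo with its 95% CI, and take the within-subgroup effects from the same model. Tie the sentence about significant differences to that contrast, or delete it.

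State the limitation in the SAP: at SD 40 the contrast has an SE of about 21 to 27 IU/L, only differences of about 58 to 75 IU/L are detectable with 80% power, and a non-significant interaction must not be read as equal effects.

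Do not extend the term to the MRE, MRI-PDFF and ALT Week 12 categories as a repair. They are defined after randomization, and for the primary endpoint the ALT category is the outcome itself, so an interaction term does not make those comparisons valid.

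The cost is a few lines of SAP text and one model term, with no new data. SAP 1 provides for an amended version before database lock.

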8.6.4.3 Exploring Relationships between Endpoints

Relationships between the endpoints will be evaluated as follows:

- Comparing the percentage change in ALT to the proportion of subjects with at least a 30% reduction in the percentage change from baseline in the MRI-PDFF score
- Comparing the percentage change in the WTH ratio to the proportion of subjects with at least a 30% reduction in the percentage change from baseline the MRI-PDFF at Week 12
- Comparing the percentage change in PRO-C3 to the proportion of subjects with at least a 30% reduction in the percentage change from baseline the MRI-PDFF at Week 12
- Comparing the percentage change in ALT to the proportion of subjects with at least a 15% reduction in the percentage change from baseline in the MRE at Week 12
- Comparing the percentage change in the WTH ratio to the proportion of subjects with at least a 15% reduction in the percentage change from baseline the MRE at Week 12
- Comparing the percentage change in PRO-C3 to the proportion of subjects with at least a 30 point reduction in ALT at Week 12
- Comparing the percentage change in body weight to the proportion of subjects with at least a 30 point reduction in ALT at Week 12
- Comparing the percentage change in PRO-C3 to the proportion of subjects with at least a 20 percent reduction in ALT at Week 12
- Comparing the percentage change in body weight to the proportion of subjects with at least a 20 percent reduction in ALT at Week 12
- Comparing the percentage change in body weight to the proportion of subjects with at least a 30% reduction in the percentage change from baseline in MRI-PDFF at Week 12
- Comparing the percentage change in body weight to the proportion of subjects with at least a 15% reduction in the percentage change from baseline in MRE at Week 12

In addition, relationships between the primary and secondary endpoints will be explored using scatterplots (and correlation coefficients) using various change and percent change from baseline. All data points will be included for all visits on a single plot, with separate color for each treatment group.

8.7 Safety analyzes

All safety analyzes will be based on the Safety population and will be performed for all safety variables specified below.

No statistical tests will be performed.

8.7.1 Adverse events

The primary safety endpoint of the study is the frequency of AEs, SAEs, and AEs leading to discontinuation through Week 12.

All Adverse Events (AEs) will be classified by Primary System Organ Class (SOC) and Preferred Term (PT) according to the Medical Dictionary for Regulatory Activities (MedDRA) Version 19.0 or higher. All subjects in the safety analysis set will be included in the summaries.

AEs will be classified as pre-treatment AEs and treatment emergent adverse events (TEAEs) and are defined as follows:

Pre-treatment AE: A pre-treatment event is any event that meets the criteria for an AE/SAE and occurs after the subject signs the ICF but before receiving the first administration of study drug.

TEAE: A TEAE is defined as an AE occurring or worsening on or after the first dose of study drug within 7 days after the last dose of study drug.

Post-treatment AE: any AE that was newly developed after the last dose date + 7 days.

Treatment-Related AEs: AE will be defined as related if causality is either probable or possible. AEs where the causality is missing will be assumed to have “Reasonable possibility of relatedness.”

Grade AEs:

Grade AEs (serious and non-serious) in accordance with the NCI/CTCAE scale (available at

https://evs.nci.nih.gov/ftp1/CTCAE/CTCAE_4.03_2010-06-14_QuickReference_8.5x11.pdf) as presented below:

- **Mild** (Grade 1) asymptomatic or mild symptoms; clinical or diagnostic observations only; intervention not indicated
- **Moderate** (Grade 2) minimal, local or noninvasive intervention indicated; limiting age-appropriate instrumental activities of daily living
- **Severe** (Grade 3) Severe or medically significant but not immediately life threatening; hospitalization or prolongation of hospitalization indicated; disabling; limiting self-care activities of daily living
- **Life-threatening** (Grade 4) Life-threatening consequences; urgent intervention indicated
- **Death** (Grade 5) Death related to the AE.

Details for imputing missing or partial start dates of adverse events are described in Section 7.2.2. Imputed Adverse Event dates will be used for determining treatment-emergence.

Summaries of AEs will include the following:

- Treatment-emergent AEs
- Treatment-emergent AEs by severity
- Treatment-emergent treatment-related AEs
- Treatment-emergent AEs leading to study drug discontinuation
- SAEs
- Treatment-related SAEs
- AEs leading to death

All TEAEs will be summarized by SOC, PT and treatment group using frequency counts and percentages. In addition, an overall summary for the categories above will be prepared by treatment group and overall. On-treatment AEs will be summarized separately from those events that occurred during treatment-free follow-up. Those events that occurred during treatment-free follow-up will be summarized by randomized treatment group. The denominator for these events will be only those subjects who entered into the 4 week treatment free follow-up period.

Where a subject has the same adverse event, based on preferred terminology, reported multiple times in the treatment period, the subject will only be counted once at the preferred terminology level in adverse event frequency tables.

Where a subject has multiple adverse events within the same system organ class in the treatment period, the subject will only be counted once at the system organ class level in adverse event frequency tables.

When reporting adverse events by severity, in addition to providing a summary table based on the event selection criteria detailed above, summary table will also be provided based on the most severe event during the treatment period - independent of relationship to study treatment.

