11.3. Analysis Populations

The following analysis populations are planned:

- **Safety Population:** All subjects who receive at least one dose of study medication. Subjects will be included in the treatment group that corresponds to the study medication received during the study.
- **Efficacy Population:** All subjects who receive at least one dose of study medication. Subjects will be included in the randomized treatment group.
- **Pharmacokinetic Population:** All subjects receiving active study medication and having any measurable plasma concentration of study medication at any timepoint.

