6 ANALYSIS POPULATIONS

6.1 Safety population

All subjects who receive at least one dose of study drug. Subjects will be included in the treatment group that corresponds to the study drug received during the study.

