8.4.1 Demographics

Subject demographics will be summarized by randomized treatment group for all subjects in the safety population. Age, height, weight and BMI at Baseline will be summarized using an 8-number summary (n, mean, standard deviation, median, 25th percentile, 75th percentile, minimum and maximum values). Qualitative variables such as gender, ethnicity and race will be summarized using count and percentage.

A by-subject listing will be provided.

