8.7.3 Clinical laboratory evaluations

Summaries of clinical laboratory results will be performed using an 8-number summary by visit and treatment. All subjects in the safety population will be included in these summaries. Baseline is defined as the last value collected prior to first dose of study drug.

The number and percentage of subjects with treatment-emergent laboratory abnormalities within 7 days of last dose of study drug will be summarized by treatment group. In addition, shift from Baseline tables will be generated by visit and treatment group. All summary tables will be repeated for abnormalities that occur during the treatment-free follow-up which is defined as occurring more than 7 days after the date of last dose. The denominator for these will include any subject who entered into the 4 week treatment-free follow-up phase.

All laboratory data will be included in the data listings and all test values outside the normal range will be flagged.

Pregnancy test and FSH will be listed separately.

The laboratory parameters listed in Table 2 on the following page will be assessed for each patient.

Creatinine clearance will be calculated by the central laboratory using the Cockcroft Gault equation and actual body weight:

$$CLCr \text{ (mL/min)} = \{((140 - \text{Age [years]}) \times \text{weight[kg]}) / (72 \times \text{SCr[mg/dL]})\} \times 0.85 \text{ (if female)}.$$

where SCr =serum creatinine

Online calculator can be found at:

https://www.kidney.org/professionals/KDOQI/gfr_calculatorCoc

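### SAP 8.7.1 groups follow-up adverse events by randomized arm, against the SAP's own rule that safety analyses go by study drug received

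*SAP*

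**What the plan says.** SAP 6.1 defines the Safety population together with its grouping rule: "Subjects will be included in the treatment group that corresponds to the study drug received during the study". Protocol 11.3 has the same rule: "Subjects will be included in the treatment group that corresponds to the study medication received during the study". SAP 8.7 then applies that population throughout: "All safety analyzes will be based on the Safety population".

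Within SAP 8.7.1, treatment-emergent events are grouped without further qualification: "All TEAEs will be summarized by SOC, PT and treatment group using frequency counts and percentages". Later in the same paragraph the follow-up events get a different rule: "Those events that occurred during treatment-free follow-up will be summarized by randomized treatment group". The next sentence gives the denominator: "The denominator for these events will be only those subjects who entered into the 4 week treatment free follow-up period". It does not say which grouping the denominator uses.

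Protocol 11.7.1 asks for adverse events by treatment group in the safety set and makes no separate provision for follow-up events.

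**The concern.** The SAP keeps the two groupings apart on purpose: drug received for the Safety and PK populations, randomized group for the Efficacy population. The word *randomized* in 8.7.1 is therefore hard to read as a loose term for the arm. A programmer following the text would use actual treatment for the on-treatment table and planned treatment for the follow-up table.

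For a subject given the wrong treatment, a late event would then be shown under a treatment the subject did not take. If the subject was randomized to placebo and took active drug, the event moves to the other side of the active-versus-placebo comparison. A reader comparing the two adverse event tables would not be told that the columns have changed meaning.

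**Working it through.** The plan states no figure on this point, so there is none to reproduce. The check is a comparison of rules, followed by a count to show the size.

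**Rules side by side**

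- All safety analyses (SAP 6.1 and 8.7; protocol 11.3): drug received.
- Treatment-emergent events (SAP 8.7.1): treatment group, unqualified. Drug received follows from 6.1 and 8.7; the paragraph itself does not repeat it.
- Follow-up events (SAP 8.7.1): randomized group, stated outright.
- Follow-up laboratory abnormalities (SAP 8.7.3): Safety population, with "The denominator for these will include any subject who entered into the 4 week treatment-free follow-up phase". No grouping is stated for follow-up, so the general rule, drug received, applies by default.

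Among the safety tables, only the follow-up adverse event table is explicitly moved to the randomized group.

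**Size**

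Inputs: planned group sizes of 25 (placebo) and 50 (2.5 mg), from SAP 3.2.1. The documents give no rate of mis-dosing, so I assume k = 0 to 3 placebo-randomized subjects who received 2.5 mg. I also assume that all subjects enter follow-up, that each of the k has one follow-up event, and that no one else in these two arms has any.

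- As written, with the denominator also by randomized group: placebo k/25, 2.5 mg 0/50.
- By drug received: placebo 0/(25 − k), 2.5 mg k/(50 + k).

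| k | As written: placebo | As written: 2.5 mg | By drug received: placebo | By drug received: 2.5 mg |
|---|---|---|---|---|
| 0 | 0/25 = 0% | 0/50 = 0% | 0/25 = 0% | 0/50 = 0% |
| 1 | 1/25 = 4.0% | 0/50 = 0% | 0/24 = 0% | 1/51 = 2.0% |
| 2 | 2/25 = 8.0% | 0/50 = 0% | 0/23 = 0% | 2/52 = 3.8% |
| 3 | 3/25 = 12.0% | 0/50 = 0% | 0/22 = 0% | 3/53 = 5.7% |

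For k = 1, the 2.5 mg minus placebo difference is 0 − 4.0 = −4.0 points as written and 2.0 − 0 = +2.0 points by drug received. If only the 22 and 44 completers targeted in SAP section 5 enter follow-up, the k = 1 figures become 1/22 = 4.5% and 1/45 = 2.2%.

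**Does this reach the primary safety endpoint?**

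That endpoint runs through Week 12 (SAP 4.3), taken here as Day 84. SAP 8.7.1 counts an event as post-treatment if it is new more than 7 days after the last dose. With last dose on Day L, such events can fall by Day 84 only if L + 7 < 84, that is, L < 77.

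- Completer, L = 84: 84 + 7 = 91, so follow-up events come after Day 91, outside the endpoint.
- Subject stopping on Day 14: 14 + 7 = 21, and the end-of-study visit is due 4 weeks after the last dose, at 14 + 28 = Day 42. Follow-up events after Day 21 and up to that visit lie inside the endpoint period.

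**The case against.** The strongest case against is that nothing happens unless a subject receives the wrong treatment, and the documents give no reason to expect that. Assignment is by IWRS, dispensed bottle numbers are recorded (protocol 5.7.1), and protocol deviations are summarized and listed (SAP 8.3), so a mis-dosed subject could be traced. SAP 8.7 rules out statistical tests on safety data, and the ALT analysis uses the randomized group throughout (SAP 6.2). All of this stands, and it limits the point to a minor one. It does not remove the contradiction: the plan sets a rule for exactly this case and then breaks it in one table.

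One might also say that nobody is on treatment during follow-up, so the randomized arm is a natural label. SAP 6.1, however, assigns subjects by the drug received during the study, which still applies after dosing ends, and 8.7.1 offers no such reason.

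Four stronger readings are tempting and are not supported:

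- **A numerator and denominator under different groupings within the follow-up table.** The denominator sentence directly follows the randomized-group sentence and refers to the same events, so one grouping for both is the natural reading. The mismatch is between tables.
- **An error in the demographics table.** SAP 8.4.1 says "Subject demographics will be summarized by randomized treatment group for all subjects in the safety population", and protocol 11.4 prescribes the same. This is an openly stated and legitimate convention, and no safety rate is computed from it.
- **Damage to the primary safety endpoint in general.** As shown above, only early discontinuers can have follow-up events inside its period.
- **One set of column Ns for all safety tables once this is corrected.** Follow-up tables count only subjects who entered follow-up, so their Ns differ by design.

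**Conclusion.** The grouping of follow-up adverse events in SAP 8.7.1 is wrong as written: it contradicts SAP 6.1, SAP 8.7 and protocol 11.3. Following it literally would split a mis-dosed subject's on-treatment and follow-up events between two dose columns.

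The effect is zero with no mis-dosing. With one placebo-randomized subject who took 2.5 mg and had one follow-up event, it is placebo 4.0% in place of 2.5 mg 2.0%, on planned group sizes with everyone entering follow-up. The number of mis-dosed subjects is an assumption. The consequence is confined to descriptive tables; no inferential result depends on it. It is worth correcting because the correction is trivial, not because the trial's conclusions are at risk.

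**What to change.** In SAP 8.7.1, replace *by randomized treatment group* with *by treatment received, as defined for the Safety population*. State that the follow-up denominator uses the same grouping. Footnote any subject whose treatment received differs from the one randomized. Leave SAP 8.4.1 unchanged, since it matches the protocol.

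The cost is one phrase, one clarifying clause and a table footnote, with no new data. The change brings the SAP back to protocol 11.3, and SAP section 1 already provides for logged changes before database lock and unblinding. The new wording does not settle how to place a subject who took more than one treatment. SAP 6.1 leaves that open, and the footnote would at least make such a case visible.
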